- A. The orphenadrine arm: Naproxen 500mg, orally twice per day + orphenadrine 100mg, orally twice per day
- B. The methocarbamol arm: Naproxen 500mg tablets, orally twice per day + methocarbamol 750mg, orally as 1 or 2 tabs, thrice per day
- C. The control arm: Naproxen 500mg tablets taken twice per day + placebo. Placebo dose will be either 1 capsule orally twice per day or 1 or 2 capsules orally, thrice per day

In an effort to maximize effectiveness while minimizing side effects, patients will be instructed to take one or two pills of the methocarbamol every 8 hours. If one tablet of the methocarbamol affords sufficient relief then there will be no need for the patient to take the second tablet. However, if the patient has not experienced sufficient relief within 30 minutes of taking one investigational medication tablet, they will be instructed to take the second tablet. Orphenadrine is only manufactured in 100mg extended release tablets and is therefore not amenable to flexible dosing. All study patients will be given 14 naproxen tablets, a seven day supply, and a sufficient number of investigational tablets to last 7 days. Optimal dosing of methocarbamol has not been established. We believe the dosing regimen we chose is sufficient to determine efficacy while not exposing patients to unnecessary risk.(8-10)

Outcome measures

1. Roland Morris LBP Disability Questionnaire (RMDQ)--Reproduced in the Appendix. This 24-item LBP functional scale is recommended for use in LBP research.(11) Its yes/ no format is amenable to telephone follow-up. We have used it successfully to obtain post-ED follow-up in five previous LBP studies involving more than 1500 patients.

2. Ordinal pain scale ("severe", "moderate", "mild", or "none"). Study participants will be asked to describe their worst back pain in the previous 24 hours.

3. Medication requirements: "Did you require any medication to treat your low back pain in the previous 24 hours?"

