4. Low back pain frequency: "Over the last 24 hours, how often were you in pain? Not at all, Rarely, Sometimes, Usually, Always". Low back pain symptomatology is quite variable. Some patients may experience no pain unless they move a certain way. Others may experience a constant low level of pain. This question will help determine the burdensomeness of the LBP in the patient's daily life.5. Satisfaction, as measured by response to this question: The next time you go to the ER with low back pain, do you want to get the same combination of medications?

Baseline measures

1. Roland Morris LBP disability questionnaire

2. Patient Health Questionnaire depression module, the PHQ 9, will be assessed at the baseline visit.

3. 5-item Cassandra questionnaire. These five questions, based on psychological variables, predict poor outcomes in an emergency room population.(12) (Reproduced in the Appendix)

4. Perceived risk of not recovering. Pain outcomes may be influenced by expectations. After providing an educational intervention, we will ask study participants to estimate how long they believe they will continue to suffer from pain.

Naproxen plus orphenadrine or methocarbamol for LBP. An RCT. Version 012716

5. StarT Back LBP questionnaire

Primary outcome

The change in Roland Morris scale between the baseline ED visit and the one week follow-up (Roland-Morris _{baseline} - Roland-Morris _{1week}). The baseline questions will refer to the time period immediately prior to ED presentation (Before you came to the ER today, were you able to....)..

Secondary outcomes

- The following outcomes will be assessed one week after ED discharge
- 1. Day post ED discharge able to return to all usual activities
- 2. Satisfaction with treatment
- 3. Number of visits to any healthcare provider.

4. Worst LBP over the previous 24 hours, using a four point ordinal scale: severe, moderate, mild, or none and a 0 - 10 verbal integer scale

5. Use of any analgesic or LBP medication within the previous 24 hours.

6. Frequency of low back pain using the five point Likert scale: Not at all, Rarely, Sometimes, Usually, Always

7.Absolute RMDQ score

The following outcomes will be assessed three months after ED discharge

1. Roland Morris Disability Questionnaire

2. Worst LBP over the previous week, using a four point ordinal scale: severe, moderate, mild, or none and a 0 - 10 verbal integer scale

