3. Frequency of low back pain over the previous week using the five point Likert scale: Not at all, Rarely, Sometimes, Usually, Always

- 4. Number of days with LBP since ED discharge
- 5. Use of any analgesic or LBP medication within the previous 7 days.
- 6. Number of visits to any healthcare provider.
- 7. Satisfaction with medication and with the current state of the LBP

Adverse events

The following adverse medication effects will be assessed at the one week follow-up.

-CNS side effects including drowsiness and dizziness

-GI side effects including dyspepsia, nausea, and bleeding

-All other side effects

Randomization and blinding

The pharmacist will perform randomization in blocks of 6 based on a sequence generated at http://randomization.com. Every block of six will contain two orphenadrine assignments, two methocarbamol assignments, one placebo assignment dosed as 1 capsule twice daily (to mirror orphenadrine dosing), and one placebo assignment dosed as 1-2 capsules thrice daily (to mirror methocarbamol dosing). Therefore, though patients will not know whether they have been assigned to active medication or placebo, they may deduce to which medication they were not assigned. This does not threaten the internal validity of the study because patients will not know whether or not they received active medication.

Naproxen will not be masked. Orphenadrine, methocarbamol, and placebo will be masked by placing tablets into identical capsules, which will be packed with scant amounts of lactose and sealed. This masking will take place in a secure location inaccessible to ED personnel. Patients will be presented with two vials of medication. The vial containing the naproxen will be labeled in a typical manner. The second vial, containing orphenadrine, methocarbamol, or placebo will be labeled as investigational medication. Patients will be instructed to the investigational medication only as needed for moderate or severe LBP.

Details of protocol

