Prior to discharge from the ED and after the patient's pain has been controlled, the attending emergency physician will refer appropriate patients to study personnel for screening. Eligible patients would have already received different and various medications in the ED for their pain (potentially including naproxen) prior to being approached for study participation. This decision is up to the attending physician and is not related to participation in the study. Patients will be screened and consented. Research associates will ascertain baseline socio-demographic information, low back pain history, and baseline variables discussed above. A urine pregnancy test will be performed. Research personnel will provide each patient with a 15-minute educational intervention. This will be based on NIAMS's Handout on Health: Back Pain information webpage (available at http://www.niams.nih.gov/Health Info/Back Pain/default.asp) Research personnel will review each section of the information sheet with the patient and elicit questions. Patients will be discharged with two medical vials, one containing naproxen and one containing placebo, orphenadrine, or methocarbamol. Patients will be cautioned not to take off protocol LBP medications without first consulting with a healthcare provider. Patients will be cautioned not to drink alcohol or use other centrally-acting substances while using study medications. Patients will be cautioned not to drive after taking the study medications. Follow-up phone calls will be conducted one week and three months after ED discharge. Follow-up will be attempted daily until successful. For patients difficult to contact, express courier or home visit will be used to obtain follow-up information. Analysis. An intention-to-treat analysis will be performed. The primary outcome will be a comparison of the change in RMDQ between baseline and one week. Results will be reported as means with 95%CI. A t-test for independent samples will be used to determine statistically significant differences

between placebo and each of the active medications. Secondary outcomes will be reported as rates with 95%CI. A per protocol efficacy analysis will be conducted among those patients who use the investigational medication at least once.

Sample size calculation

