We based assumptions on a recently completed RCT of LBP treatment. The mean improvement in RMDQ among those who receive naproxen alone was 10.2. The standard deviation was 8.9. A widely accepted minimum clinically important improvement of 5 points on the RMDQ would require those randomized to active medication to demonstrate a mean improvement of 15.2 on the RMDQ. Using a standard alpha of 0.05 and a beta of 0.20, we determined the need for 50 subjects in each arm. To account for protocol violations and patients lost-to-follow-up (typical lost-to-follow-up rate is 5%) and to ensure sufficient power for the per protocol analysis (in our previous ED-based LBP studies, up to 1/3 of enrolled patients have not used the medication more than once), we intend to enroll 80 patients in each arm.

Data Safety Monitoring Committee. This committee will be headed by [name] and include XXX. The committee will meet every month with the PI to 1) monitor adverse events and develop strategies to minimize these; and, 2) monitor recruitment and enrollment. There will not be an interim analysis. Naproxen plus orphenadrine or methocarbamol for LBP. An RCT. Version 012716 6

Registration. The study will be registered at http://www.clinicaltrials.gov.

Consent. Study personnel will obtain informed consent once the patient's pain has been controlled and the patient is ready for discharge from the ED.

Risks/Benefits

Non-steroidals are used in 50% of more than 2.5 million annual US ED visits for LBP. Skeletal muscle relaxants are used in 43% of these visits. Regardless of results, this study will have a national impact. Study subjects will benefit by receiving a medication that is likely to improve their acute LBP. In addition to breach of confidentiality, which is unlikely, and inconvenience to the subject, which will undoubtedly occur, it is likely that subjects will experience adverse medication effects. For the most part, these are nuisance events. Skeletal muscle relaxants such as orphenadrine and methocarbamol are generally well tolerated but can cause substantial drowsiness and when combined with alcohol or other centrally acting substances may be lethal. Non-steroidals can cause life-threating gastro-intestinal bleeding, but this is unlikely in patients screened for gastro-intestinal illness who will take the medication for one week only.

Data Storage & Confidentiality

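### Does testing each drug against one placebo arm that mixes two dosing schedules undermine the comparison?

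*Combined protocol and SAP*

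**What the plan says.** - **Study arms, C** defines one control arm with two placebo schedules: "Placebo dose will be either 1 capsule orally twice per day or 1 or 2 capsules orally, thrice per day".
- **Randomization and blinding** allocates, in every block of six, two orphenadrine, two methocarbamol and one placebo on each drug's schedule. It concedes that the schedule lets a patient rule out one drug, and then states: "This does not threaten the internal validity of the study because patients will not know whether or not they received active medication". The same section tells patients to use the investigational capsules "only as needed for moderate or severe LBP".
- **Details of protocol, Analysis** plans t-tests on the change in RMDQ "between placebo and each of the active medications", with no distinction by schedule. The only further efficacy analysis is per protocol, in patients who used the investigational medication at least once.
- **Sample size calculation**: "Using a standard alpha of 0.05 and a beta of 0.20, we determined the need for 50 subjects in each arm"; to allow for losses and non-use, "we intend to enroll 80 patients in each arm".

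The protocol never uses the word pooled. One control arm, 80 patients per arm and the wording of the test leave no other natural reading.

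**The concern.** The placebo capsules are matched to each drug's schedule, yet the analysis ignores the matching. Half of orphenadrine's comparator takes capsules on methocarbamol's schedule, and the reverse. The schedules differ visibly: one fixed capsule twice daily, against one or two capsules thrice daily with a second capsule if relief is insufficient. The outcome is self-reported.

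If the schedule itself shifted the RMDQ, the combined comparison would mix drug effect with schedule effect. It would flatter one drug and penalise the other by the same amount. The sentence on internal validity argues only from blinding, so it seems to leave this possibility open. At stake would be a false claim of benefit for one drug and lost power for the other.

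**Working it through.** **Inputs.** From Sample size calculation: SD 8.9, difference 5 points, alpha 0.05, beta 0.20, 50 evaluable and 80 enrolled per arm, 5% loss, and up to one third of patients not using the medication more than once. From Randomization and blinding: allocation 2:2:1:1. The protocol gives no effect of schedule on RMDQ. Call it *s*; the range of 0 to 3 points below is an assumption.

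**1. The plan's own figure.** Two-sided: n = 2 × [8.9 × (1.960 + 0.842) / 5]² = 49.7, so 50 per arm, as stated. Enrolment: 50 / (0.95 × 2/3) = 78.9, consistent with 80. The calculation takes the whole placebo arm as comparator, so design and analysis agree.

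**2. Blinding.** Per block, the twice-daily schedule holds 2 orphenadrine and 1 placebo; the thrice-daily schedule holds 2 methocarbamol and 1 placebo. The chance of active drug is 2/3 on both. The schedule reveals which drug a patient did not get, but not whether the capsule is active.

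**3. Precision with no schedule effect.** Analysed: 80 × 0.95 = 76 per arm, 38 per placebo half.
- Combined: SE = 8.9 × √(1/76 + 1/76) = 1.44; power for 5 points 93%.
- Schedule-matched: SE = 8.9 × √(1/76 + 1/38) = 1.77; power for 5 points 80%.

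Both powers are from the noncentral t. With *s* = 0 both estimates are unbiased and the combined one is better.

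**4. What an assumed *s* would do.** The placebo arm is a 1:1 mix, so the combined estimate is off by *s*/2, in opposite directions for the two drugs. These figures take the target to be the drug effect net of schedule, and *s* to be additive and the same with active and inert capsules.

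| Assumed *s* (points) | Bias | Two-sided rejection, null drug | Power for true 5 points, penalised drug |
|---|---|---|---|
| 0 | 0 | 5.0% | 93% |
| 1 | 0.5 | 6.4% | 87% |
| 2 | 1.0 | 10.6% | 79% |
| 3 | 1.5 | 17.8% | 67% |

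The lower two rows require the timing and number of capsules alone to move the RMDQ by 2/5 = 40% or 3/5 = 60% of the plan's clinically important difference.

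**5. Break-even.** Mean squared error is 1.444² + *s*²/4 = 2.084 + *s*²/4 for the combined estimate and 1.768² = 3.127 for the matched one. They are equal at *s* = √[4 × (3.127 − 2.084)] = 2.04 points. In a per-protocol set with one third excluded (76 × 2/3, about 51 per arm) the break-even is about 2.5 points. One third is a pessimistic figure there, because it counts patients who did not use the medication more than once, while the set drops only those who never used it.

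**6. What a matched analysis could show.** For either drug, the matched and combined estimates differ by half the difference between the placebo halves. With no schedule effect that gap has SD = ½ × 8.9 × √(2/38) = ½ × 2.04 = 1.02 points. A true *s* of 2 would move it by 1.0 point, about one SD, so chance and a schedule effect could hardly be told apart. Comparing the placebo halves directly (38 v 38) gives a 95% CI of about ±4.1 points and 16% power for 2 points.

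**The case for a change.** The strongest case for acting is this. The outcome is self-reported and the regimens look different to the patient. The protocol itself remarks, under Baseline measures, "Pain outcomes may be influenced by expectations". The matched placebo groups are already randomised, and a matched contrast would keep the 80% power that the plan aims for. Pre-specifying it costs a few lines, whereas the same analysis done later would be post hoc.

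The facts in that case stand: no schedule-matched contrast is planned, and the assumption of no schedule effect is not written down. The inference to a defect does not.

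- The remark on expectations introduces a baseline question, put to all participants, on how long they expect their pain to last. It says nothing about capsule number or frequency. Expectation of active drug is equal on the two schedules, as step 2 shows.
- The validity sentence answers the point directly before it, that a patient may rule out one drug. It gives a blinding reason for a blinding question, and the reason is correct. Its wording is broad, but narrowing it would be an edit.
- The matched placebos are not wasted. They keep the masking intact, and every planned comparison relies on that.
- As-needed use, and the investigators' experience in previous trials that up to one third of patients did not use the medication more than once, reduce any real difference in intake between schedules. The as-needed instruction and the daily schedules under Study arms should be reconciled with each other, but that is a separate matter.
- The matched groups are fixed by the randomisation, so an own-schedule contrast added later would leave little room for analyst choice.

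**Conclusion.** The concern does not hold. Followed as written, the plan gives a sound comparison on everything the protocol shows: blinding to active versus placebo is preserved, the sample size matches the single placebo arm, and the combined test is unbiased if the schedule of inert capsules has no effect. It is also the more precise choice (SE 1.44 against 1.77 points) and has the smaller mean squared error unless a schedule effect exceeds about 2.0 points in the intention-to-treat set, or about 2.5 in a per-protocol set that loses one third.

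The bias and error rates above zero rest entirely on an assumed effect for which the documents give no evidence. A schedule-matched analysis would leave the primary test and its conclusion unchanged, and its result would be hard to read, since it would differ from the combined result by chance with an SD of about 1.0 point. Adding it is a matter of preference. The conclusion assumes SD 8.9, 76 analysed per arm and a two-sided 5% test; the protocol does not state sidedness, but two-sided reproduces its 50 per arm.

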- Absence of non-musculoskeletal etiology of low back, such as urinary tract infection, ovarian cysts, or influenza like illness. The primary clinical diagnosis, at the conclusion of the ED visit, must be a diagnosis consistent with non-traumatic, non-radicular, musculoskeletal LBP.

-Patient is to be discharged home. Patients admitted to the hospital are more likely to be treated with parenteral medication and therefore are not appropriate for this study.

- Age 18-69 Enrollment will be limited to adults younger than 70 years because of the increased risk of adverse medication effects in the elderly.

-Non-radicular pain: pain cannot radiate below the gluteal folds in a radicular pattern. Patients with non-radicular pain extending below the gluteal folds will not be excluded

-Pain duration ≤ 2 weeks (336 hours). Patients with more than two weeks of pain are at increased risk of poor pain and functional outcomes.(2)

-Prior to the acute attack of LBP, back pain cannot have occurred once per month or more frequently. Patients with more frequent back pain are at increased risk of poor pain and functional outcomes.(2)

-Non-traumatic LBP: no substantial and direct trauma to the back within the previous month -Functionally impairing back pain: A baseline score of > 5 on the Roland-Morris Disability Questionnaire (Appendix)

Exclusion criteria:

-Not available for follow-up

-Pregnant or breast-feeding

-Chronic pain syndrome defined as use of any analgesic medication on a daily or near-daily basis -Allergic to or intolerant of investigational medications

-Contra-indications to non-steroidal anti-inflammatory drugs: 1) history of hypersensitivity to NSAIDs or aspirin or patients in whom NSAIDS or aspirin have induced allergic manifestations such as asthma, nasal polyps, rhinitis, or urticarial 2) active or history of peptic ulcer disease, chronic dyspepsia, or active or history of gastrointestinal bleed 3) Severe heart failure (NYHA 2 or worse) 4) hypertension (JNC7 stage 2 or worse) 5) Chronic kidney disease 3 or worse 6) Current use of anti-coagulants, bleeding with tooth brushing, easy bruisability 7) Hepatitis 8) Alcoholism

Naproxen plus orphenadrine or methocarbamol for LBP. An RCT. Version 012716

-Contra-indications to orphenadrine: 1) Glaucoma, Prostatic hypertrophy, Myasthenia gravis, Pyloric or duodenal obstruction

-Contra-indications to methocarbamol: 1) Myasthenia gravis, Chronic kidney disease 3 or worse

Study arms:

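### Free improvement: the t-test on RMDQ change is valid, but fitting baseline RMDQ as a prespecified covariate costs almost nothing and may narrow the confidence interval

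*Combined protocol and SAP*

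**What the plan says.** Under Primary outcome, the endpoint is "The change in Roland Morris scale between the baseline ED visit and the one week follow-up", computed as baseline minus week 1. Baseline RMDQ is also the first item under Baseline measures, and it describes the patient before the ED visit: "The baseline questions will refer to the time period immediately prior to ED presentation". The Inclusion criteria require "A baseline score of > 5 on the Roland-Morris Disability Questionnaire", so on the 24-item scale entry scores run from 6 to 24.

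The Analysis paragraph (within Details of protocol) states that "An intention-to-treat analysis will be performed", that results are given as means with 95% CI, and that "A t-test for independent samples will be used to determine statistically significant differences" between placebo and each active arm. No covariate, regression or ANCOVA is mentioned. Randomization and blinding describes blocks of six, with no stratification by baseline RMDQ.

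The Sample size calculation uses a control-arm mean improvement of 10.2, a 5-point target and an SD: "The standard deviation was 8.9". It arrives at 50 per arm and enrols 80, partly to protect the per-protocol analysis, because in earlier studies "up to 1/3 of enrolled patients have not used the medication more than once".

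**The concern.** Subtracting baseline fixes its coefficient at 1. That is the most precise use of baseline only if week-1 RMDQ rises one point, on average, for each extra point at baseline. At any other slope, variance that baseline could explain stays in the error term and the confidence intervals are wider than they need to be. Seen after the fact, the same thing appears as a fraction (1 − b) of any chance baseline difference between arms passing into the treatment estimate. These are two views of one cost.

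The documents give a reason to expect some dependence of change on baseline. Improvement cannot exceed the baseline score. A patient who enters at 6 to 10 cannot improve by the 10.2 points assumed for the control arm, and one who enters at 15 or below cannot improve by the 15.2 targeted for an active arm. If such patients are enrolled, change cannot behave alike at every baseline. How strong the dependence is cannot be learned from the documents.

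Only precision is at stake. The validity of the comparison is not in question.

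**Working it through.** **Inputs from the documents.** Difference 5 points; SD 8.9, read as the SD of change (variance 79.21); alpha 0.05, taken as two-sided; 50 per arm required; 80 per arm enrolled; 5% loss to follow-up; up to one third with little or no use of study drug.

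**Inputs assumed.** Baseline SD 4 to 6; slope b of week-1 on baseline RMDQ 0.25 to 1. Neither is in the documents.

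**The plan's own figure.** n = 2 × 8.9² × (1.960 + 0.842)² / 5² = 49.7, so 50 per arm. This reproduces the plan and confirms the two-sided reading (one-sided gives 40). With the exact t distribution, 50 per arm gives 79.4% power.

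**Evaluable numbers.** Intention-to-treat: 80 × 0.95 = 76 per arm. Per-protocol worst case: 80 × 0.95 × 2/3 = 50.7, taken as 50.

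**Unadjusted test.** At 76 per arm, SE = 8.9 × √(2/76) = 1.44, 95% CI half-width 2.85, power 93.1%. At 50 per arm, SE = 8.9 × √(2/50) = 1.78, half-width 3.53, power 79.4%.

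**Adjusted analysis.** With the SD of change held at 8.9, the residual variance given baseline is 79.21 − (1 − b)² × SD_base². For example, with SD_base = 5 and b = 0.5 it is 79.21 − 0.25 × 25 = 72.96, a fall of 7.9%. Power is from the noncentral t distribution.

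| Baseline SD, b | Variance reduction | Power, 76/arm | Half-width, 76/arm | Power, 50/arm | Half-width, 50/arm |
|---|---|---|---|---|---|
| any, 1 | 0% | 93.1% | 2.85 | 79.4% | 3.53 |
| 4, 0.75 | 1.3% | 93.4% | 2.83 | 79.9% | 3.51 |
| 6, 0.75 | 2.8% | 93.7% | 2.81 | 80.6% | 3.48 |
| 4, 0.5 | 5.0% | 94.2% | 2.78 | 81.4% | 3.44 |
| 5, 0.5 | 7.9% | 94.8% | 2.74 | 82.6% | 3.39 |
| 6, 0.5 | 11.4% | 95.5% | 2.69 | 84.0% | 3.33 |
| 6, 0.25 | 25.6% | 97.9% | 2.46 | 89.7% | 3.05 |

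**Chance imbalance is the same component.** At 76 per arm, the part of the baseline difference that reaches the unadjusted estimate has SD (1 − b) × SD_base × √(2/76). This is 0.32 for (4, 0.5) and 0.73 for (6, 0.25). Squared and divided by the squared SE of 1.44, these give 5.0% and 25.6% (before rounding), the same as the variance reductions.

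**Cost if b = 1.** Estimating the slope with three arms inflates variance by an expected 1/(3n − 5): 1/223 = 0.45% at 76 per arm and 1/145 = 0.69% at 50. Pooling the error variance over three arms adds degrees of freedom that offset this, so power stays at 93.1% and 79.4%. With two arms at a time the inflation is 1/(2n − 4), and power is 92.9% and 79.0%.

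**Type I error.** In 20,000 simulated trials (baseline SD 5, b 0.5, 76 per arm) the rejection rate under the null was 0.052 for the t-test and 0.051 for the adjusted model.

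**The case against.** The strongest reply is that nothing is broken. Endpoint, test and sample size are consistent with one another, and the choice is between two valid analyses. That is right, and is why this is offered as an improvement only.

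The gain also rests on assumed inputs. The 26%, 97.9% and 89.7% figures belong to the most favourable corner of the range and should not be repeated as expected gains. Nor is the range a bound: b = 0 with a baseline SD of 6 would give 36/79.21 = 45%. At b = 0.5 the intention-to-treat half-width narrows by only 0.07 to 0.17 points, in a comparison that already has 93.1% power. This stands.

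The per-protocol figure needs care. The Sample size calculation counts patients who did not use the drug more than once, whereas the Analysis paragraph keeps anyone who used it at least once. On the latter definition the set is at least 50.7 per arm, and larger if some patients took a single dose. Fifty is a floor under the plan's own allowances. That set is also selected on use after randomisation, so the assurance of unbiasedness does not carry over to it, and adjusting for baseline RMDQ does not restore it.

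The three-arm model pools the error variance, which separate t-tests do not require. The two-arm results above show that the cost stays small without pooling, about 0.2 to 0.4 percentage points of power.

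Finally, absolute week-1 RMDQ is already a secondary outcome. Differences in change and in absolute score bracket the adjusted estimate for any fitted b between 0 and 1, so a reader could see the effect of a baseline imbalance. That does not recover the lost precision.

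**Conclusion.** The point holds as a free improvement. The t-test on change is valid, and 50 evaluable and 80 enrolled per arm need no revision. Prespecified adjustment for baseline RMDQ costs at most about 0.4 percentage points of power, and none to one decimal in the three-arm model. In return, the residual variance falls by 0% to 26% under the assumed ranges: nothing at b = 1, 1% to 3% at b = 0.75, and 5% to 11% at b = 0.5. The gain is of most use in the per-protocol analysis, where the worst case leaves about 79% power and no reserve. Confidence in the size is medium, because the baseline SD and slope are assumed and 8.9 is read as the SD of change. The conclusion concerns only the use of baseline. Multiplicity across the two comparisons and missing week-1 scores are separate matters.

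**What to change.** Before unblinding, replace the t-test sentence in the Analysis paragraph with one that names a single linear model on all three arms as primary: week-1 RMDQ on treatment arm and baseline RMDQ, with baseline as a linear term. Modelling change instead gives the same treatment effect, so the planned comparison of mean change is kept. Report the two adjusted active-versus-placebo differences with 95% CI, show the unadjusted means as description, and keep the t-test as a sensitivity analysis. Use the same model for the per-protocol set and for 3-month RMDQ.

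The cost is one sentence. Baseline RMDQ is already needed to compute the primary outcome, so no data are added, no patient is lost and the sample size is unchanged. The covariate must be fixed in advance, since adding it after results are known would look like a choice made on them.
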